Smoking history, in/outpatient, past and current history of Crohn's disease, height, weight, duration of illness, complications, past illnesses, and history of allergy.

2) Previous anti-TNF α treatment of Crohn's disease

Presence/absence, history, and reasons for discontinuation of anti-TNF α treatment.

3) Previous drug treatment of Crohn's disease (treatment during the 3-month period prior to the investigation)

Presence/absence and contents of previous treatment of Crohn's disease

4) Treatment with Humira

At the time of first administration: method of administration, initial dose, and date of initial administration.

At the second administration: method of administration, dosage, and date of second administration

At the third administration and thereafter: method of administration, dosage, interval of administration, duration of administration, and reasons for change in dose or interval of administration.

Patients performing self-injection: presence/absence of written consent for transition to

self-injection, and presence/absence of self-injection transition record.

5) Treatment with antituberculosis agents

Presence/absence of antituberculosis agents, names of drugs, daily dose, and duration

6) Status of administration of concomitant drugs

Presence/absence of concomitant drug use for Crohn's disease, name of drug, route, dose, and duration.

7) Usage of non-drug treatment for Crohn's disease

Presence/absence and type of non-drug treatment, and duration.

8) Presence/absence of development of tuberculosis or serious infections

Day of examination, imaging technique, presence/absence of abnormal laboratory findings, and description of abnormal findings.

9) Crohn's Disease Activity Index (CDAI)

Evaluate at baseline and week 4, month 3, month 6, year 1, year 1.5, year 2, year 2.5 and year 3 of Humira treatment, and at the time of discontinuation of the treatment

10) Work Productivity and Activity Impairment Questionnaire: Crohn's disease (WPAI: CD)

Evaluate at baseline and week 4, month 3, month 6, year 1, year 1.5, year 2, year 2.5 and year 3 of Humira treatment, and at the time of discontinuation of the treatment.

11) C-reactive protein (CRP)

Evaluate at baseline and week 4, month 3, month 6, year 1, year 1.5, year 2, year 2.5 and year 3 of Humira treatment, and at the time of discontinuation of the treatment

12) Endoscopic examination

Date (baseline, during treatment and year 3 or after discontinuation) and endoscopic findings

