9.5. Statistical test method

The test does not include the classification of unknown/not provided. In principle, the first layer is subjected to the intersegmental test of classified data. Multiplicity is not adjusted.

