	
medication, exclude the case from the calculation for concomitant medication. If the above imputing methods do not help add the date (the first administration date or the final administration date is not provided, etc.), or if the first administration date and the final administration date of concomitant medication are reversed, it should be regarded as a concomitant medication.
 
(‘Clear’ refers to a condition where no ambiguous expressions like “around”, “in the middle”, etc. are included and a number or figure only is provided.)

Concomitant medication: aminosalicylic acid products	See the drug code list and determine from the drug codes.
Concomitant medication: corticosteroid	See the drug code list and determine from the drug codes.
Concomitant medication: immunosuppressant	See the drug code list and determine from the drug codes.
Concomitant medication: antibiotics	See the drug code list and determine from the drug codes.
Concomitant medication: others	Others are the drugs other than aminosalicylic acid products, corticosteroid, immunosuppressant, and antibiotics.
Prior medication: TNF α drug	
When presence/absence treatment history with anti-TNFα drug is “present” in “treatment history with anti-TNFα drug for Crohn’s disease” of the survey form, it should be classified as “with” the history. When the assessment is impossible based on the checkbox, it should be classified as “unknown” whereas no description should be “not provided”. Other cases are “without” the history.

Prior medications	
When a patient had a prior medication of TNFα drug and any of the prior-medication type checkboxes is checked, the patient is regarded as “with prior medications”. When the assessment is impossible based on the checkbox of presence/absence of prior medication/treatment, regard it as “unknown” while no description should be “not provided”. Other cases are “without” prior medications.

Data name	Derivation and calculation methods
Prior medication: aminosalicylic acid products	If aminosalicylic acid drug in the survey form is checked, regard the case as “with aminosalicylic acid drug”. Others are “without aminosalicylic acid drug”.
Prior medication: corticosteroid	If corticosteroids in the survey form is checked, regard the case as “with corticosteroids”. Others are “without corticosteroids”.

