Prior medication: immunosuppressant	If immunosuppressant in the survey form is checked, regard the case as “with immunosuppressant”. Others are “without immunosuppressant”.
Prior medication: antibiotics	Otherwise, when antibiotics in the survey form is checked, regard the case as “with antibiotics”. Others are “without antibiotics”.
Prior treatment	When any of the checkboxes of each prior-treatment type in “prior medication/treatment for Crohn's disease is checked in the survey form, regard it as “with prior treatment”. When the assessment is impossible based on the checkbox of presence/absence of prior medication/therapy, regard it as “unknown” while no description should be “not provided”. Other cases are “without” prior treatment.
Prior treatment: surgery	Refer to “[Humira CD Long] Conversion data provided for analysis” to identify it.
Prior treatment: granulocyte and monocyte adsorption apheresis (GCAP)	When GCAP is checked in the survey form, regard it as “with GCAP”. Others are “without GCAP”.
Prior treatment: enteral nutrition therapy	When enteral nutrition therapy is checked in the survey form, regard it as “with enteral nutrition therapy”. Others are “without enteral nutrition therapy”.
Prior treatment: intravenous nutrition therapy	When intravenous nutrition therapy is checked in the survey form, regard it as “with intravenous nutrition therapy”. Others are “without intravenous nutrition therapy”.
Concomitant therapy	It should be described in “non-medicinal treatment/concomitant therapy for Crohn's disease” of the survey form. The data from the first administration date to the final administration date of Humira will be calculated. When concomitant-therapy data are contained under the same rule as the definition of concomitant medications defined in “10.1 General”, regard it “with concomitant therapy”. When “presence/absence of concomitant therapy” in the survey form is not assessable, select “unknown” while it is not provided, select “not provided”. Other cases are “without

Data name	Derivation and calculation methods
	concomitant therapy”.
Concomitant therapy: surgery	Refer to “[Humira CD Long] Conversion data provided for analysis” to identify it.
Concomitant therapy: GCAP	When GCAP is checked in the survey form, regard it as “with GCAP”. Others are “without GCAP”.

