Dose period	the first administration to Week 4 of administration, after Week 4 of administration to Month 3 of administration, after Month 3 of administration to Month 6 of administration, after Month 6 of administration to Year 1 of administration, after Year 1 of administration to Year 1 and Month 6 of administration, after Year 1 and Month 6 of administration to Year 2 of administration, after Year 2 of administration to Year 2 and Month 6 of administration, after Year 2 and Month 6 of administration to Year 3 of administration, Continued as of Year 3 of administration
Reason for discontinuation	Development of adverse event, lack of effectiveness, patient's wish, no visit, others
Sex	Man, women, unknown/not provided
Pregnancy/nursing	Not pregnant/nursing, pregnant, nursing, unknown/not provided
Age (in years)	<15, ≥15 and <65, ≥65, unknown/not provided
Body weight (kg)	<30, ≥30 and <40, ≥40 and <50, ≥50 and <60, ≥60, unknown/not provided
BMI(kg/m ²)	<18.5, ≥18.5 and <25, ≥25 and <30, ≥30, unknown
Duration of illness (in	<2, ≥2 and <5, ≥5 and <10, ≥10, unknown/not provided

Data	How to stratify
years)	
Indication	Crohn's disease, other, unknown/not provided
Allergy history	Without the history, with the history, unknown/not provided
Smoking history	Without the history, with the history, unknown/not provided
Details of smoking history	Smoking, only in the past (not smoking now), unknown
HBs antigen	Not conducted, conducted, unknown/not provided
Tuberculosis-test status	Not conducted, conducted
Complications	Without the history, with the history, unknown/not provided
Detailed classification of complications	Liver disorder, renal disorder, blood disorder, respiratory disorder, others
Other classification of complications	Diabetes mellitus, osteoporosis, malignant tumour, others
Medical history	Without the history, with the history, unknown/not provided
Detailed classification of medical history	Tuberculosis, non-tuberculous mycobacteriosis, interstitial pneumonia, bronchitis bacterial, aplastic anaemia, pancytopenia, malignant tumour, others
Prior medications for Crohn's disease	Without the history, with the history, unknown/not provided
Detailed classification of prior medications for Crohn's disease	Anti-TNF α drug, aminosalicylic acid products, corticosteroid, immunosuppressant, and antibiotics.
Prior treatment for Crohn's disease	Without the history, with the history, unknown/not provided

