Calculate the number of patients and the percentage to the number of patients surveyed per number of patients surveyed, number of patients with adverse reactions, etc. number of adverse reactions, type of adverse reactions, etc. (SOC, PT).

Note: Aggregate the initial reactions among the identical PTs in a patient. Aggregate the events based on the segments which contain the initial onset period of adverse reactions among Time Allowance defined in “12.4 Assessment period for the onset status of adverse reactions”. When calculating the number of patients with the target reactions, remove overlapped data per case number and onset period. When calculating the number of SOC, remove the overlapped data per case number, onset period and SOC.

Count the number of target patients and reactions by using the dates defined below until the assessment period applicable to Time Allowance defined in “12.4 Assessment period for the onset status of adverse reactions”.

- Discontinued patients: the final administration date of Humira + 28 days
- Not discontinued patients: the first administration date of Humira + 1120 days

Even if there is one adverse reaction, it should be counted as one patient in every period when the reaction persisted.

“2.9 Incidence of adverse reactions (serious adverse reactions/adverse reactions) per background factor”

Patients for analysis: patients in the safety analysis group

Analysis objective: to show the incidence of adverse reactions per patient background factor and analyze them.

Analysis items: calculate the number of all patients, the percentage to the number of patients with serious adverse reactions and all patients, the number of patients with adverse reactions and the percentage to number of all patients, the tests for adverse reactions (Fisher's exact test for nominal-scale factors and Man-Whitney's u test for ordinal-scale factors) per the following patient background factor regarding the adverse reactions which occurred in the safety analysis period. Note that the test does not include the patients "with treatment history with anti-TNF α drug for Crohn's disease".

Note: the patient background factors are as follows:

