Sex, age (year), body weight (kg), BMI (kg/m²), duration of illness (year), indication (registration form), allergy history, smoking history, with smoking history (details), self-administration, tuberculosis test status, hepatitis B virus test status (registration form), complication, complication: liver disorder, complication: renal disorder, complication: blood disorder, complication: respiratory disorder, complication: diabetes mellitus, complication: osteoporosis, complication: malignant tumour, medical history, medical history: tuberculosis, medical history: non-tuberculous mycobacteriosis, medical history: interstitial pneumonia, medical history: bronchitis bacterial, medical history: aplastic anaemia, medical history: pancytopenia, medical history: malignant tumour, prior medication for Crohn's disease, prior medication: anti-TNF α drug, prior medication: aminosalicylic acid drug, prior medication: corticosteroids, prior medication: immunosuppressant, prior medication: antibiotics, prior treatment for Crohn's disease, prior treatment: surgery, prior treatment: GCAP, prior treatment: enteral nutrition therapy, prior treatment: intravenous nutrition therapy, treatment history with anti-TNF α drug for Crohn's disease, with treatment history with anti-TNF α drug for Crohn's disease, concomitant medication, concomitant medication: aminosalicylic acid drug, concomitant medication: corticosteroids, concomitant medication: immunosuppressant, concomitant medication: antibiotics, concomitant therapy for Crohn's disease, concomitant therapy: surgery, concomitant therapy: GCAP, concomitant therapy: enteral nutrition therapy, concomitant therapy: intravenous nutrition therapy, site of disease: anus/perianal region, site of disease: rectum, site of disease: stomach/duodenum, site of disease: colon, site of disease: jejunum/ileum, intestinal complication, non-intestinal complication, work condition, CDAI when the administration was started, CRP

"2.9.xx Incidence of adverse reactions per background factor and seriousness"

Patients for analysis: patients in the safety analysis group

Analysis objective: to show the onset status of non-serious/serious adverse reactions per statistically-significant background factor based on the test results in 2.9.

Analysis item: aggregate the following items per background factor and seriousness for adverse reactions which occurred in the safety analysis period.

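### The SAP's 'and' rule for prior medications counts anti-TNF-naive patients with prior steroids, immunosuppressants, aminosalicylates or antibiotics as having had none

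*SAP*

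**What the plan says.** The entry for prior medications in SAP 10.1 joins two conditions. If the patient had a prior TNFα "drug and any of the prior-medication type checkboxes is checked, the patient is regarded as" having prior medications. 'Unknown' is reserved for a presence/absence box that cannot be assessed, and 'not provided' for no entry. The rest are swept up by "Other cases are “without” prior medications".

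Three other parts of the SAP treat the same information differently:

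- **Drug-class items (10.1).** Aminosalicylates, corticosteroids, immunosuppressants and antibiotics are each set by their own tick, with no anti-TNF condition.
- **Section 11.** The detailed classification of prior medications lists anti-TNF drugs and then "aminosalicylic acid products, corticosteroid, immunosuppressant, and antibiotics", all at the same level under one parent.
- **Prior treatment (10.1).** This entry begins "When any of the checkboxes of each prior-treatment type in" and needs nothing more than one ticked type.

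The parent row is a background factor in table 1.12 (section 13.1), table 2.9 (13.2) and table 3.4.1 (13.3). The last two apply Fisher's exact or Mann-Whitney tests. Table 2.9.xx is then produced for each "statistically-significant background factor based on the test results in 2.9".

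**The concern.** Programmed as written, the rule makes prior anti-TNF use a precondition for having had any prior medication. A parent category can then hold fewer patients than one of its own sub-classes, which is impossible if the parent means what its name says. A reader of the regulatory report would take the negative group as previously untreated, when many of its members had recent steroids or immunosuppressants.

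A test of this row in 2.9 or 3.4.1 is mostly a second test of anti-TNF history, which already has its own row. Because 2.9.xx depends on significance in 2.9, the coding could trigger a breakdown or cause one to be missed.

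A smaller wording point sits in the same tables. The note in 2.9 and 3.4.1 opens "Note that the test does not include the patients" and then gives what is actually the name of a sub-row in the factor lists. SAP 9.5 says "In principle, the first layer is subjected to the intersegmental test of classified data", so the likelier meaning is that this one sub-row is not tested. Read literally, the note would remove every anti-TNF-experienced patient from all the tests and leave the anti-TNF history factors with a single level.

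**Working it through.** **The rule, case by case.** For patients whose presence/absence box can be assessed:

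| Prior anti-TNF | Any type box ticked | As written ('and') | With 'or' |
|---|---|---|---|
| yes | yes | with | with |
| yes | no | without | with |
| no | yes | **without** | with |
| no | no | without | without |

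The third line is the definite error: the same patient is positive on a drug-class row and negative on the parent. The second line matters only if anti-TNF is not itself one of the type boxes. The form is not available to settle that, although Protocol 8(3) collects anti-TNF history and other prior drugs as separate items. A patient with unknown anti-TNF history and a ticked steroid box also falls into 'without', because the 'unknown' branch looks only at the prior medication/treatment box.

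**Size.** The plan states no figure to reproduce, and the documents give neither prevalence below, so both are assumptions.

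- p = anti-TNF-naive share, taken as 0.3 to 0.5.
- q = share with another prior drug, taken as 0.7 to 0.9 and equal in naive and experienced patients.
- n = 300 (planned for investigation) to 500 (registered), from the sample-size sections; 400 lies midway.
- Unknown and not-provided cases are ignored.

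Naive patients wrongly coded 'without' = p × q:

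| p | q | Share | n = 300 | n = 400 | n = 500 |
|---|---|---|---|---|---|
| 0.3 | 0.7 | 0.21 | 63 | 84 | 105 |
| 0.5 | 0.7 | 0.35 | 105 | 140 | 175 |
| 0.3 | 0.9 | 0.27 | 81 | 108 | 135 |
| 0.5 | 0.9 | 0.45 | 135 | 180 | 225 |

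A wider range, p = 0.4 to 0.8 with q = 0.7 to 0.9, gives 300 × 0.4 × 0.7 = 84 up to 300 × 0.8 × 0.9 = 216 of 300.

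**What the row then measures**, if anti-TNF is not a type box:

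- 'Without' under 'and' = p + (1 − p)(1 − q). At q = 0.9 this is 0.30 + 0.07 = 0.37 and 0.50 + 0.05 = 0.55.
- 'Without' under 'or' = p(1 − q). At q = 0.9 this is 0.03 and 0.05; at q = 0.7 it is 0.09 and 0.15.
- Agreement of the 'and' row with anti-TNF history = 1 − (1 − p)(1 − q). At q = 0.9 this is 0.93 and 0.95; at q = 0.7 it is 0.79 and 0.85.

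If anti-TNF is one of the type boxes, the 'and' row equals anti-TNF history exactly.

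**The case against.** The strongest reply is that this is a translation slip. The English is loose elsewhere: tables 3.2.1.2 and 3.2.2.3 describe the non-remission subgroup as being in remission, and only the stated objective corrects it. The entry draws on two parts of the form, and 'and' may mean the two sources taken together. Section 11 points to that intent, and nothing shows how the rule was programmed. That explains the wording but does not repair it. The SAP uses 'or' and 'and' deliberately in its definition of the tuberculosis test, so a programmer would reasonably code this entry as a conjunction.

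The second reply is that the consequence is small, and much of this stands. It is one summary row among more than fifty factors in a single-arm survey with no multiplicity adjustment. Each drug class has its own correct row, and the priority safety outputs (2.4.1.1, 2.4.1.2, 2.4.2) do not use it. A 2.9.xx breakdown triggered by the 'and' row would largely repeat one that anti-TNF history could trigger itself. The 'or' row might have only 9-15 of 300 patients in its 'without' group (3-5%), so its test would rarely reach significance.

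The third reply is that the size rests entirely on assumed prevalences. That is true, and agreement with anti-TNF history falls to 79-85% at the lower value of q. Even so, the row remains mostly a repeat.

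**Conclusion.** The concern holds. The definition is wrong as written: it contradicts section 11 and the drug-class items, departs from the any-box approach used for prior treatment, and is not overridden anywhere else. That conclusion rests on the text alone and needs no assumed figure.

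The size does depend on assumptions. Across the main range, roughly a fifth to just under half of all patients would be misclassified on this row. The effect is confined to the parent row in 1.12, 2.9 and 3.4.1 and to any 2.9.xx table that it triggers. It should be corrected, but it does not threaten the survey's main safety results. The claim about patients whose only prior drug was an anti-TNF stays conditional on the form, and the note in 2.9 and 3.4.1 is a matter of clarity only.

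**What to change.** 1. In SAP 10.1, replace 'and' with 'or', so that a patient has prior medications if there was a prior anti-TNF drug or any prior-medication type box is ticked.
2. Add a programming check that the parent count is at least as large as each sub-class count.
3. Footnote the row in 1.12, 2.9 and 3.4.1. Anti-TNF history has no stated look-back, whereas Protocol 8(3) limits other prior drugs to "treatment during the 3-month period prior to the investigation".
4. Reword the note in 2.9 and 3.4.1 to say that no test is done for the sub-row on patients with an anti-TNF history, and that these patients stay in all other tests.

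The cost is one word in one derivation, one simple check, one footnote and one reworded note, with three tables affected. The drawback is that the corrected row combines two look-back periods and may have a very small 'without' group (3-5% at q = 0.9, 9-15% at q = 0.7), so its test may say little. Its main value is a correct description of the patients.

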Presence/absence of administration of anti-hepatitis B virus agent	If the following drug codes are included in the survey form, regard the case as “with administration of an anti-hepatitis B virus agent”. Others are “without administration of an anti-hepatitis B virus agent”. Entecavir (Baraclude): 6250029 Tenofovir (Tenofovir, Viread): 6250024 Adefovir (Hepsera): 6250026 Lamivudine: 6250006, 6250020
Presence/absence of allergy history	When allergy data are contained in the survey form, it should be classified as “with allergy history”. When the checkbox of ‘medical history unknown’ is checked, it should be ‘unknown’ while no

Data name	Derivation and calculation methods
	description should be ‘not provided’. Others are “no allergy history”.
Presence/absence of smoking history	When the checkbox of ‘with’ smoking history is checked in the survey form, regard it as ‘with’ smoking history. When the checkbox of ‘no’ smoking history is checked in the survey form, regard it as ‘without’ smoking history. When the checkbox of ‘unknown’ for smoking history is checked in the survey form, regard it as ‘unknown’. If nothing is described in the survey form, it should be ‘not provided’.
Details of smoking history	For the items for smoking history in the survey form, when the ‘smoking’ checkbox is checked or when the smoking years column is checked of the ‘smoking’ checkbox, regard it as “smoking”. When smoking “in the past” is checked other than “smoking” or when the smoking years for “in the past” is provided, regard it as “only in the past”. When a case is not applicable to “smoking” or “only in the past” though a smoking history exists, regard it as “unknown”.
Administration status	
[1] 1st administration: as a patient with a dose of 160mg
 
[2] 2nd administration: 2nd administration date - the first administration date = 14 days \pm4 days or less, and a patient with a dose of 80mg.
 
[3] 3rd administration: 3rd administration date - the 2nd administration date = 14 days \pm4 days or less, and a patient with a dose of 40mg.
 
[4] 4th administration and thereafter: the dosing frequency “once every 2 weeks” is checked in the survey form, and a patient with a dose of 40mg
 
* If the patient receives the fourth administration and thereafter, all the administration status should be the condition as shown in [4].

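### Ten treatment-detail factors in SAP 10.1 have no 'unknown' level, so patients with an unknown or blank parent item are tested as unexposed

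*SAP*

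**What the plan says.** SAP 10.1 (General) defines ten detail rows with two levels only:

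- Prior medication, four rows. For corticosteroids: "If corticosteroids in the survey form is checked, regard the case as “with corticosteroids”. Others are “without corticosteroids". The rows for aminosalicylates, immunosuppressants and antibiotics close in the same way: "Others are “without aminosalicylic acid drug", "Others are “without immunosuppressant" and "Others are “without antibiotics".
- Prior treatment, three rows: granulocyte and monocyte adsorption apheresis (GCAP), enteral nutrition and intravenous nutrition. For GCAP: "When GCAP is checked in the survey form, regard it as “with GCAP”. Others are “without GCAP".
- Concomitant therapy, three rows: the same three therapies, with the same rule.

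The three parent rows in the same table (prior medications, prior treatment, concomitant therapy) are built differently. Each has an 'unknown' level for an answer that cannot be assessed and a 'not provided' level for a blank.

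SAP 9.5 says of testing: "The test does not include the classification of unknown/not provided". SAP 9.2 states the same exclusion for categorical data. All ten detail factors are on the tested lists of chart 2.9 (adverse reactions) and chart 3.4.1 (CDAI remission at final assessment), where nominal factors are compared by Fisher's exact test.

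**The concern.** The exclusion in 9.2 and 9.5 can act only on a level that the derivation creates, and these ten rows create none. One patient can therefore be treated in two ways within one chart: absent from the test of the parent factor because the answer is unknown, and present in the tests of its components as a confirmed non-user.

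The 'without' group then contains some patients who were in fact exposed. With non-informative missingness this weakens any real association. With informative missingness it can weaken, create or reverse one. The practical consequence is in chart 2.9, because the factors significant there receive the detailed breakdown by seriousness in the 2.9.xx tables. A coding rule could thus add or remove a factor from that set.

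**Working it through.** **1. Row count.** 4 prior medications + 3 prior treatments + 3 concomitant therapies = 10. Each appears by name among the 61 entries listed for chart 2.9 and again for chart 3.4.1.

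**2. Comparison with sibling rows.** In SAP 10.1 the five complication subtypes, the seven medical-history subtypes and the anti-TNF history row all define 'unknown' and 'not provided'. SAP section 11 lists the complication and medical-history subtypes without an unknown class, yet 10.1 gives them one. The section 11 layout therefore does not explain the omission in the ten rows.

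**3. Who is affected.** If the parent question was answered, an unticked box is a fair 'without'. The misclassification is limited to patients with no box ticked whose parent item is 'unknown' or 'not provided'.

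**4. Size under missing at random.** The plan gives no missing share, exposure prevalence or adverse-reaction rate, so there is no figure of its own to reproduce and all rates below are assumptions. Let u be the share with an unknown or blank parent and p the true exposure prevalence. The 'without' group consists of true non-users with an answer, (1−p)(1−u), plus everyone with a missing answer, u. The share of it that is truly exposed is

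c = u·p / [(1−p)(1−u) + u].

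With risks r1 (exposed) and r0 (unexposed), the apparent risk in 'without' is c·r1 + (1−c)·r0. The observed difference is therefore (1−c)(r1−r0), and c is the proportional shrinkage of the risk difference.

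| Missing u | p = 30% | p = 50% | p = 70% |
|---|---|---|---|
| 2% | 0.006/0.706 = 0.8% | 0.010/0.510 = 2.0% | 0.014/0.314 = 4.5% |
| 5% | 0.015/0.715 = 2.1% | 0.025/0.525 = 4.8% | 0.035/0.335 = 10.4% |
| 10% | 0.03/0.73 = 4.1% | 0.05/0.55 = 9.1% | 0.07/0.37 = 18.9% |
| 20% | 0.06/0.76 = 7.9% | 0.10/0.60 = 16.7% | 0.14/0.44 = 31.8% |

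**5. Effect on the test, missing at random.** Fisher's exact test, two-sided 5%, was simulated with 2,000 runs per scenario: N = 300 or 500, 30% or 50% exposed, and true risks of 30% against 20% (risk ratio 1.50). Across 5–20% missing, the recoding shrinks the expected risk ratio to between 1.48 and 1.39. At N = 500 and 50% exposed, power with exclusion against recoding is 0.691 and 0.673 at 5% missing, and 0.608 and 0.529 at 20% missing. Exclusion had the higher power in all 12 scenarios, despite its smaller denominators.

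**6. Effect when missingness is related to recorded events.** Take no true effect (20% risk in both groups), 50% exposed and 20% missing.

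- Missing patients with half the recorded risk: apparent risk in 'without' = (0.40×0.20 + 0.20×0.10)/0.60 = 0.167, risk ratio 0.20/0.167 = 1.20.
- Missing patients with one and a half times the risk: (0.40×0.20 + 0.20×0.30)/0.60 = 0.233, risk ratio 0.20/0.233 = 0.86.

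The direction therefore depends on an unknown. For the half-risk case, the simulated type I error with recoding is about 4–5% at 5% missing. It reaches 11–14% at 20% missing with 50% exposed. With exclusion it stays at about 4–5% throughout.

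**The case against.** The case on the other side is substantial on size.

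- **Missingness may be low.** The protocol (section 6(3)) has the sponsor check the forms and reinvestigate where necessary. Only locked forms are analysed (SAP section 8), and unassessable safety, unassessable effectiveness and doubtful data credibility are grounds for exclusion (chart 1.3.1). None of this creates the missing level, but it argues against a large residual share, and the table shows little effect at 2–5% except where exposure is high.
- **Under-recording of events is not established.** SAP 10.2 also takes adverse events from the detailed investigation when they are not on the survey form. Poorly completed forms need not mean fewer recorded events. This stands, and it is why no direction of bias is claimed.
- **The tests are exploratory.** They cover 61 listed factors without multiplicity adjustment. The malignancy and serious-infection charts (2.4.1.1 to 2.4.2), the overall incidences and the overall remission rates do not use these ten factors. This also stands.

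A reader might infer that allergy history has the same error, because its 'unknown' level is taken from another item: "When the checkbox of ‘medical history unknown’ is checked, it should be ‘unknown". The documents do not support that. A blank allergy entry is already 'not provided' and leaves the test. Whether an unknown allergy can be recorded separately depends on the survey form, which is not in the documents; with one shared 'unknown' box the rule would be correct.

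**Conclusion.** The inconsistency is real and follows from the text alone: ten derivations bypass the exclusion that SAP 9.2 and 9.5 prescribe, while comparable rows in the same table respect it. Its size cannot be fixed from the documents. Under missing at random the risk difference shrinks by about 1–4% at 2% missing, 2–10% at 5%, 4–19% at 10% and 8–32% at 20%, over exposure of 30–70%. The inflated type I error needs both a high missing share and informative missingness, and both are assumptions.

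Two stronger readings should be avoided. The rule does not misclassify every unticked box, only those under an unanswered parent. Nor does it threaten the survey's main safety results; what it can change is the screening in charts 2.9 and 3.4.1 and the choice of 2.9.xx tables. The surgery rows (external conversion file) and the concomitant-drug rows (drug codes) are outside this conclusion, because the documents do not show how they treat a missing parent.

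**What to change.** In each of the ten rows, add one condition: if the detail box is not ticked and the parent item is 'unknown' or 'not provided', assign that parent level to the detail row. SAP 9.2 and 9.5 then remove the patient from that test with no further rule. A ticked box remains 'with' whatever the parent says.

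The cost is one derivation line per row, no new data, and slightly smaller test denominators (for example, 0.05 × 500 = 25 patients if 5% of 500 were affected). Since 9.2 keeps unknown answers in the denominator of descriptive percentages, the percentage 'with' in chart 1.12 does not change. Reporting the number of patients moved in each row would show whether the matter was of any size.

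For allergy, the sponsor need only confirm whether the form has its own unknown entry and, if it does, use that entry instead of the medical-history box.
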